## **STUDY PROTOCOL. Elkar laguntza**

### AIMS

The general aim of the present research will be to evaluate the effectiveness of a peer social support intervention in cancer patients at the Onkologikoa Foundation of Guipuzcoa. Specifically, the immediate and long-term effect that such intervention will have on symptoms of psychological distress, quality of life, coping strategy, perception of social support, perception of the disease and emotional regulation will be evaluated. As a secondary aim of this study, we intend to evaluate the immediate and long-term effect of the peer social support intervention on the immune system (through the determination of the levels of cytokines IL-1 $\beta$ , IL-2, IL-6, IL-8, IL-10, IFN- $\gamma$  and TNF- $\alpha$ ), on the monoaminergic system (through the determination of plasma levels of serotonin, tyrosine, phenylalanine, tryptophan, quinurenine, quinurenic acid and 3-HK), on the HPA axis (through the measurement of the diurnal cycle of cortisol), and on sex hormones (through the measurement of estradiol and testosterone levels), systems that have been related both to the development of anxious-depressive symptoms and to the development, progression and recurrence of cancer.

In addition, it will be studied at what time the application of the program is most effective, being applied in newly diagnosed patients (experimental group 1) and in patients who have just finished medical treatment (experimental group 2).

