Each of the volunteers will have to be with 2 or 3 patients at the same time since some authors state that performing support to more than one patient can compensate for a poor relationship with another patient, as well as serve as support in the event of a patient's death (Moulton et al., 2013). The volunteer-patient sessions will be conducted in rooms set up for this purpose in the Carlos Santamaría building of the UPV/EHU. After each session with the patients, each volunteer will have to attend an individual session with the program coordinator [name] to discuss their emotions and reactions after performing the intervention. Psychological supervision of the volunteers is a fundamental part of avoiding retraumatization and the possible appearance of anxious-depressive symptoms (Giese-Davis et al., 2006). Likewise, volunteers will have to participate in group sessions every two months with the rest of the volunteers and the program coordinator [name] in order to strengthen group cohesion, resolve doubts, detect needs and carry out the necessary training.

The patients in this study will be 120 patients with various types of cancer from the Onkologikoa Foundation. Each patient will be matched with a volunteer depending on the type of tumor and medical treatment, since some authors state that for the support program to be effective, the volunteers must have had the same type of tumor and medical treatment as the patients (Pistrang et al., 2012). This is why it will be necessary to homogenize the group of volunteers as much as possible so that the sample of patients has as little variability as possible. The inclusion criteria are: having received the diagnosis of cancer in the last month; not having started medical treatment; the tumor type and medical treatment coinciding with any of the volunteers. The exclusion criteria are: relapse; suffering or having suffered from a serious mental disorder (according to DSM-V criteria). The recruitment of these patients will take place just after the diagnosis, and the professionals of the Onkologikoa Foundation will be in charge of offering this type of intervention to the patients who meet the inclusion criteria of the study.

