## VARIABLES

The sociodemographic and clinical variables to be collected are: age, marital status, employment status, language, family situation, clinical history of interest, personal and family history of psychopathology, pharmacological, psychological and substance use treatment, tumor type, stage and medical treatment.

The psychological variables will be assessed by means of the following questionnaires: Big-5 brief personality questionnaire, HADS anxiety and depression questionnaire, COPE-28 coping questionnaire, brief illness perception questionnaire, MOS-SSS social support questionnaire, SF-12 quality of life questionnaire, resilience scale, ERQ emotional regulation scale and the program satisfaction questionnaire.

The biological variables to be determined are:

- In blood: levels of cytokines related to tumor development and inflammation (IL1 $\beta$ , IL-2, IL-6, IL-8, IL-10, IFN- $\gamma$  and TNF- $\alpha$ ); monoaminergic activity (tyrosine, phenylalanine, tryptophan, quinurenine, serotonin, quinurenic acid and 3HK) and IDO activity (through the tyrosine-kinurenine ratio).
- In saliva: the diurnal cortisol cycle and estrogen and testosterone levels.

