#### DATA ANALYSIS

The relationships between the variables collected will be analyzed with the SPSS version 22.0 statistical package and with the JMP 10 statistical package. In all the analyses performed, the following variables will be controlled: type and duration of medical treatment and pharmacological treatment. Repeated measures analyses will be performed to study the effect of the intrasubject support program. Also, in order to study the possible physiological and psychological differences between experimental groups 1 and 2, analysis of variance (ANOVA) will be carried out. Pearson's correlation coefficient will be used to analyze the relationships between the different physiological and psychological variables considered in this study. Several General Linear Models (GLM) analyses will be performed to determine the predictive value of each of the variables in the possible benefit obtained after the application of the program. To study the interactions in each of the GLM analyses performed, a simple regression analysis will be carried out.

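### Sex hormones are outcomes with no sex restriction on entry, yet sex is neither listed nor controlled: hormone correlations can be confounded, and a single-visit group ANOVA loses precision

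*Combined protocol and SAP*

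**What the plan says.** - **Outcome.** The secondary aim in AIMS covers the intervention's effect "on sex hormones (through the measurement of estradiol and testosterone levels"). VARIABLES confirms the measurement: "In saliva: the diurnal cortisol cycle and estrogen and testosterone levels".
- **Sample.** METHODS states: "The patients in this study will be 120 patients with various types of cancer from the Onkologikoa Foundation". The inclusion criteria, which end by requiring a match with a volunteer, read: "having received the diagnosis of cancer in the last month; not having started medical treatment; the tumor type and medical treatment coinciding with any of". Exclusions are relapse and serious mental disorder. None refers to sex.
- **Collected variables.** The list in VARIABLES opens with "age, marital status, employment status, language, family situation" and goes on to clinical history, psychopathology, treatments, tumour type and stage. Sex is not in it.
- **Analysis.** DATA ANALYSIS fixes the adjustment set for all analyses: "the following variables will be controlled: type and duration of medical treatment and pharmacological treatment". It then plans repeated-measures analyses within subjects, ANOVA between the two experimental groups, Pearson correlations between physiological and psychological variables, and general linear models for predictors of benefit.

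Sex is not named as a stratification factor for the block randomisation, nor among the matching variables in METHODS.

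**The concern.** Sex is an obvious source of variation in testosterone and estradiol levels. A plan that measures both, does not restrict sex and fixes its covariates without sex is exposed in two ways.

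1. **Confounding of associations.** The correlations between hormones and psychological scores are observational, so randomisation does not protect them. If men and women differ in both a hormone and a score, pooling them yields a correlation even when there is none within either sex. The predictor models have the same weakness. A plain sex difference could then be reported as a hormone-distress link.
2. **Loss of precision.** In an ANOVA of hormone levels between the groups at one evaluation, the difference between the sexes sits in the error term and makes a real effect of the programme harder to see.

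**Working it through.** The documents give N = 120 but no significance level, SD, effect size or sex mix, so the plan has no figure to reproduce. What follows is an illustration.

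**Inputs**
- From the documents: N = 120.
- Assumed: minority-sex share p = 0.1, 0.3 or 0.5; hormone difference between the sexes D = 1, 2 or 3 within-sex SDs; difference in a distress score d = 0.2 to 0.6 within-sex SDs; equal within-sex SDs; no correlation within either sex; two-sided 5% test.

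**Formulas**
- Outcome variance with sex ignored, relative to the within-sex variance: V = 1 + p(1−p)D².
- Equivalent sample size: 120 / V.
- Spurious correlation: r = p(1−p)Dd / √[(1 + p(1−p)D²)(1 + p(1−p)d²)].
- Chance of p < 0.05: Fisher z, with mean atanh(r) × √117 against 1.96.

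**Worked extremes**
- Smallest (p = 0.1, D = 1, d = 0.2): V = 1 + 0.09 = 1.09; r = 0.018 / √(1.09 × 1.0036) = 0.017; chance of significance 5.4%.
- Largest (p = 0.5, D = 3, d = 0.6): V = 1 + 0.25 × 9 = 3.25; r = 0.45 / √(3.25 × 1.09) = 0.239; chance of significance 75%.

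| p | D | V | 120/V | r for d = 0.2 to 0.6 | chance of p < 0.05 |
|---|---|---|---|---|---|
| 0.1 | 1 | 1.09 | 110 | 0.02 to 0.05 | 5% to 9% |
| 0.1 | 2 | 1.36 | 88 | 0.03 to 0.09 | 6% to 17% |
| 0.1 | 3 | 1.81 | 66 | 0.04 to 0.12 | 7% to 25% |
| 0.3 | 1 | 1.21 | 99 | 0.04 to 0.11 | 7% to 22% |
| 0.3 | 2 | 1.84 | 65 | 0.06 to 0.18 | 10% to 50% |
| 0.3 | 3 | 2.89 | 42 | 0.07 to 0.21 | 13% to 65% |
| 0.5 | 1 | 1.25 | 96 | 0.04 to 0.13 | 8% to 29% |
| 0.5 | 2 | 2.00 | 60 | 0.07 to 0.20 | 12% to 61% |
| 0.5 | 3 | 3.25 | 37 | 0.08 to 0.24 | 15% to 75% |

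At p = 0, V = 1 and r = 0.

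**Power.** Assume 60 per arm and a true effect of 0.5 within-sex SD. Power is 78% with sex adjusted. Without it, at D = 2, power is 65%, 52% or 49% for p = 0.1, 0.3 or 0.5. Over the whole grid it runs from 75% down to 33%.

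**How far the precision loss reaches.** The V column applies only to a single-visit ANOVA that uses neither sex nor baseline. Suppose baseline were a covariate, with an assumed within-sex correlation of 0.5 between baseline and follow-up. The residual variance is 0.75 with sex in the model, and V − (0.5 + p(1−p)D²)²/V without it. At p = 0.5 the latter is 0.80, 0.875 or 0.923 for D = 1, 2, 3. The ratios are 1.07, 1.17 and 1.23, equivalent to about 112, 103 and 98 patients. A change score removes a stable sex difference entirely.

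**The case against.** The strongest reply is that the hormone aim largely survives. AIMS asks for the intervention's effect on the hormones. The link with anxious-depressive symptoms appears there as background, not as an aim. The groups are randomised, so leaving sex out does not systematically bias their comparison. Hormones are measured at five evaluations, and the planned repeated-measures contrasts cancel stable sex differences. All of this stands. A reader might infer that the sex-hormone aim cannot be answered, or that variation between the sexes drowns the group contrast. The documents do not support either reading, and with D = 1 and equal numbers the loss is only from 120 to 96.

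A second reply is that the sample may turn out to be nearly single-sex. Patients must match a volunteer's tumour type, and the protocol means to "homogenize the group of volunteers as much as possible so that the sample of patients has as little variability as possible". That makes the mix uncertain, so the point must be conditional. But no single sex or tumour type is named, the sample is still described as having various cancers, and METHODS refers to participants with both pronouns.

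Third, treatment type is controlled and tumour type is collected, and both carry some information about sex. The illustration gives them no credit and so may overstate the effect. They are imperfect proxies, though, and tumour type is not in the adjustment set. Sex is probably in the medical record, so the accurate statement is that it is not listed. Having it on file would not put it in the models.

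None of these replies repairs the pooled correlations. DATA ANALYSIS does not say that the ANOVA uses baseline, so the precision point also remains for a single-visit comparison.

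**Conclusion.** The point holds, conditionally on both sexes enrolling, which is likely but not stated. The main harm is to the hormone-psychological correlations and the predictor models, where sex can act as a confounder. The lesser harm is lost precision in an unadjusted single-visit ANOVA.

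Under the assumptions listed, the spurious correlation ranges from about 0.02 to 0.24, with roughly 5% to 75% of trials of 120 reaching significance where 5% is nominal. The variance inflation ranges from 1.09 to 3.25. The upper ends need an even sex split, a 3 SD hormone difference and, for the correlation, a 0.6 SD distress difference. With a 10% minority the correlation harm is modest. In a single-sex sample there is none.

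The matter concerns two salivary markers among many secondary ones. It is worth correcting because the remedy is small.

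**What to change.** - In VARIABLES, list sex as a baseline variable.
- In DATA ANALYSIS, add sex as a covariate in the hormone ANOVA and in the general linear models that involve hormones.
- Report hormone-psychological correlations as partial correlations given sex. Give results by sex only where each sex has enough patients.
- If the sample is in fact meant to be single-sex, say so in the eligibility criteria. The point then falls away.

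The cost is one data field, SAP wording and one degree of freedom per model. Sex may overlap with treatment type, which is already controlled, so some coefficients may be estimated less precisely.

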For each GE1 patient, a specific volunteer will be selected based on the patient's tumor type and medical treatment, although depending on the availability of volunteers, other variables will also be taken into account: age, preferred language, time availability, partner, children and socioeconomic level. Once selected, each patient and volunteer will be given a letter of introduction to the other, in order to learn basic information about the patient before the first session. The social peer support program will begin the week prior to the start of medical treatment. There will be a total of eight sessions, one every fifteen days approximately, for a total duration of four months. The duration of each session will be as follows: the first and second sessions will last approximately one hour, the following sessions will last an average of 30 minutes. Patients and volunteers will be given the possibility to request a change of person in case they feel that the bond between them is not adequate.

Once the support program has been completed in EG1, a second evaluation of clinical, psychological and biological variables will be carried out, and, in addition, satisfaction with the intervention program will be evaluated, thanks to the Treatment Satisfaction Questionnaire. In GE2, the evaluation of clinical, psychological and biological variables will be carried out four months after the first evaluation. A third evaluation of all participants will be carried out 15 days after receiving the news of the end of the medical treatment (chemotherapy or radiotherapy). At four months and eight months after the end of medical treatment (chemotherapy or radiotherapy), the fourth and fifth evaluations will be carried out. In each of these evaluations the procedure will be as follows: each participant will be given a questionnaire of psychological measures to fill in before their appointment and four saliva collection tubes, which they will have to collect the day before their appointment. In addition, they will be scheduled for a blood draw and for the collection of the questionnaires and saliva samples.

GE2 patients will participate in the peer support program, but the application of this intervention will take place 15 days after receiving the news of the end of medical treatment. The intervention in this group will have the same characteristics and the same evaluations as those of GE1.

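### The programme's effect is assigned to within-patient repeated measures, and the randomised EG1 versus EG2 contrast at evaluation 2 is not named as the test of effectiveness

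*Combined protocol and SAP*

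**What the plan says.** The general aim in AIMS is effectiveness, specifically "the immediate and long-term effect that such intervention will have on symptoms of psychological distress" and on several other psychological outcomes. A further aim gives the two groups a different role: "it will be studied at what time the application of the program is most effective, being applied in newly diagnosed patients (experimental group 1") or in patients who have just finished treatment (experimental group 2).

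METHODS randomises patients in balanced blocks after evaluation 1. For EG1, "The social peer support program will begin the week prior to the start of medical treatment", and "There will be a total of eight sessions, one every fifteen days approximately, for a total duration of four months". EG2 starts the programme 15 days after the news that medical treatment has ended.

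Evaluation 2 is anchored differently in the two arms. For EG1, "Once the support program has been completed in EG1, a second evaluation of clinical, psychological and biological variables will be carried out"; for EG2 it falls four months after evaluation 1. Evaluations 3 to 5 are timed from the end of medical treatment in both arms.

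Three sentences in DATA ANALYSIS matter here:
- On the programme's effect: "Repeated measures analyses will be performed to study the effect of the intrasubject support program".
- On the groups: "in order to study the possible physiological and psychological differences between experimental groups 1 and 2, analysis of variance (ANOVA) will be carried out".
- On covariates: "In all the analyses performed, the following variables will be controlled: type and duration of medical treatment and pharmacological treatment".

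None of the three names a visit or says which analysis decides whether the programme works.

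**The concern.** The only analysis that the plan ties to the programme's effect appears to be change within patients. In EG1 that change runs from shortly after diagnosis into cancer treatment. In EG2 the programme period follows the end of treatment. Distress, quality of life and the biological markers may well move over those periods without any support. Recovery could make an ineffective programme look effective in EG2, and worsening under treatment could hide a real benefit in EG1.

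The trial has the means to avoid this. At evaluation 2 the randomised arms differ mainly in having had the programme or not, but the plan does not say that this comparison answers the main aim. The choice of visit also changes the question: by evaluation 5 both arms have had the programme, so an EG1 versus EG2 difference there speaks only to early versus late support.

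**Working it through.** The plan gives 120 patients with no alpha, power, effect size, SD or dropout, so there is no stated calculation to reproduce. The figures below illustrate the mechanism; they do not estimate the bias in this trial.

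**Inputs.** From METHODS: 120 patients and balanced randomisation. Assumed: 60 per arm, two-sided 0.05, no dropout, outcome SD 1 at each visit, and correlation ρ = 0.5 between evaluations (range 0.3 to 0.7).

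**Step 1: within-arm paired test when the programme does nothing.** The SD of change is √(2(1 − ρ)), which is 1.0 at ρ = 0.5. With drift d, the noncentrality is d√60 / √(2(1 − ρ)) on 59 df.

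| Drift (SD) | Noncentrality, ρ = 0.5 | Significant, ρ = 0.5 | Range, ρ = 0.3 to 0.7 |
|---|---|---|---|
| 0.1 | 0.1 × 7.746 = 0.775 | 12% | 10–17% |
| 0.2 | 1.549 | 33% | 25–50% |
| 0.3 | 2.324 | 63% | 49–84% |

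A simulation of 20,000 trials gave 11.9%, 33.0% and 62.5% at ρ = 0.5.

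**Step 2: randomised contrast, same conditions.** A drift common to both arms cancels in EG1 minus EG2. In the same simulation the test of change between arms rejected in 4.7% to 5.4% of trials, whatever the drift.

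**Step 3: do the planned covariates rescue the within-patient analysis?** No. They explain differences between patients around the average change, not the average change itself. In a separate simulation of 10,000 trials (drift 0.3 SD, ρ = 0.5) the paired test rejected in 62.9% of trials both with and without mean-centred treatment type and duration.

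**Step 4: power of the evaluation 2 contrast for a true 0.5 SD benefit.**
- Unadjusted: noncentrality 0.5 / √(2/60) = 2.739 on 118 df, power 78%.
- Adjusted for the evaluation 1 score: residual SD √(1 − ρ²) = 0.866, noncentrality 0.5 / (0.866 × √(2/60)) = 3.162 on 117 df, power 88% (81–97% for ρ = 0.3 to 0.7).
- Pre-post paired test with no drift: noncentrality 0.5 × 7.746 = 3.873 on 59 df, power 97%.
- Paired test when EG1 worsens by 0.3 SD under treatment: net change 0.5 − 0.3 = 0.2 SD, so 33%, as in Step 1.

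**Step 5: unequal timing at evaluation 2.** Suppose drift is 0.3 SD per four months, or 0.075 SD per month. If EG1 is seen one or two months later than EG2, the arms differ by 0.075 or 0.15 SD with no programme effect. The adjusted contrast then rejects in 8% or 16% of trials.

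**Step 6: EG2 patients who start before evaluation 2.** EG2's session eight falls 15 + 7 × 15 = 120 days after the end-of-treatment news, and that news comes after evaluation 1. Taking four months as 120 days, no EG2 patient can have had all eight sessions by then. If 10% or 20% of EG2 had half the benefit by that visit, the contrast shrinks to 0.475 or 0.45 SD and adjusted power to 85% or 81%.

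**The case against.** The strongest reply is that the valid comparison is already within the plan. The groups are randomised, an EG1 versus EG2 ANOVA is written down, and EG2 is evaluated at four months, matching the stated length of the programme. All of that stands. An ANOVA at evaluation 2 would be valid even unadjusted; baseline adjustment only adds precision. A reader might infer that the plan has no between-group analysis, or that a confounded answer is inevitable. The documents support neither. What is missing is the visit and the role of that comparison.

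The key sentence is also unclear English. The word intrasubject is attached to the programme, and a repeated-measures model can carry a group factor. A model without groups is the likelier reading, because the next sentence deals with the groups separately, but it remains an inference.

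Two further readings go too far:
- **Treatment duration.** One might infer that the covariate rule blocks an evaluation 2 analysis because duration is still unknown for patients on treatment. No analysis is scheduled at that visit, and duration will be known at final analysis for patients followed to the end of treatment. The narrower point stands: duration is fixed after randomisation.
- **Non-completers.** One might infer that EG1 patients who miss sessions have no evaluation 2. Completion of the programme can also mean the end of the four-month period. This needs clarifying; it is not a written bar.

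Finally, no figure in the documents supports any particular drift. At 0.1 SD the false-positive rate is 12%, much less striking than 63%. The confounding does not depend on the size of the drift, but the harm does.

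**Conclusion.** The concern holds in this form: the programme's effect is assigned to what is most likely a within-patient analysis, and the randomised contrast that could answer the main aim has neither a visit nor an effectiveness role. This is more than missing detail, because the analysis that the text does point to cannot separate the programme from the course of disease and treatment, while randomised data that can will exist.

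Under the stated assumptions, a within-arm test with no programme effect is significant in 12% to 63% of trials for a drift of 0.1 to 0.3 SD. The evaluation 2 contrast stays near 5% provided drift is equal in both arms, which requires similar timing of that visit. An evaluation 5 comparison is not wrong in itself: it addresses the plan's timing aim, but it cannot stand in for a comparison of the programme with no programme.

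**What to change.** 1. State that effectiveness is judged by the EG1 minus EG2 difference at evaluation 2, with all patients as allocated and adjusted for the evaluation 1 score (ANCOVA, or group by visit in a mixed model). Treat within-group changes as descriptive.
2. In this analysis use only covariates known at evaluation 1, as an exception to the general covariate sentence, because treatment duration is fixed after randomisation.
3. State that EG1 patients who do not complete the sessions are still assessed at evaluation 2. Reconcile the two timing anchors for that visit (programme completion versus four months after evaluation 1), and report elapsed time by arm.
4. Report how many EG2 patients began the programme before evaluation 2, and keep them as allocated.
5. Describe comparisons made after EG2 starts the programme as early versus late support.

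No new visits or patients are needed, but there are costs:
- Power at 0.5 SD is 88%, against 97% for a pre-post test free of drift.
- Any EG2 patients who start early dilute the contrast (Step 6).
- A common visit date is a trade-off. At 15-day spacing, session eight comes 7 × 15 = 105 days after session one. With a visit 120 days after evaluation 1, EG1 patients who start more than 15 days after evaluation 1 would be seen before session eight, which weakens the measurement of the immediate effect in them.

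### Treatment is to be controlled in every analysis, but the biology–psychology associations rest on Pearson correlations with no stated adjustment for treatment or randomised group

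*Combined protocol and SAP*

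**What the plan says.** DATA ANALYSIS opens with a general rule: "In all the analyses performed, the following variables will be controlled: type and duration of medical treatment and pharmacological treatment". A few lines later it names the method for associations: "Pearson's correlation coefficient will be used to analyze the relationships between the different physiological and psychological variables considered in this study". It does not mention partial correlation, residuals or stratification. It does not call the correlations unadjusted, and it does not exempt them from the general rule. It also does not say at which evaluation, or in which randomised group, they are computed.

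On the sample, METHODS states: "The patients in this study will be 120 patients with various types of cancer from the Onkologikoa Foundation". It also asks for a homogeneous set of volunteers "so that the sample of patients has as little variability as possible". At entry a patient must qualify as "not having started medical treatment". Four further evaluations follow: one at about four months, one 15 days after news that treatment has ended, and two more at four and eight months after its end. EG1 receives the programme from the week before treatment starts. EG2 starts it 15 days after the news that treatment has ended.

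Among the data to be collected, VARIABLES lists "pharmacological, psychological and substance use treatment, tumor type, stage and medical treatment". Treatment duration is not listed separately.

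**The concern.** A Pearson coefficient relates two variables and leaves no place for a third. Anything that moves both a biomarker and a questionnaire score will produce a correlation between them, even when the two are unrelated among patients on the same treatment. This design has two obvious candidates.

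- **Treatment.** Patients have different tumours and treatments. The plan's own decision to control for treatment shows that it expects treatment to matter.
- **The programme.** From the second evaluation until EG2 completes its sessions, the groups differ in exposure to an intervention intended to change psychological state and tested for biological effects. Group is not on the controlled list, so even an analyst who applies the general rule faithfully would leave this source in.

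At stake is the interpretation of the association results. AIMS motivates the biological measurements by noting that these systems have been related to anxious-depressive symptoms. A reader will take the correlations as evidence on that link.

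**Working it through.** The plan states no alpha, effect size or power for these analyses, so there is no figure of its own to reproduce. The check asks how large the distortion could be.

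**Inputs**
- From METHODS: N = 120. Complete data are assumed.
- Assumed: two-sided alpha 0.05; two treatment types with share p = 0.5 or 0.3 on one of them; a shift of d SD on both measures, with d from 0.2 to 1.0; true correlation zero within treatment type.

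**Induced correlation.** A binary factor that shifts both measures by d within-group SDs adds p(1−p)d² to the covariance and to each variance, so

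r = p(1−p)d² / (1 + p(1−p)d²).

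For p = 0.5 and d = 0.8: 0.25 × 0.64 = 0.16, and r = 0.16/1.16 = 0.138.

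**False-positive rates** (20,000 simulated trials per row; standard error at most about 0.35 percentage points)

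| p | d (SD) | induced r | plain Pearson | partial correlation |
|---|---|---|---|---|
| 0.5 | 0.2 | 0.010 | 4.7% | 4.8% |
| 0.5 | 0.5 | 0.059 | 9.7% | 5.0% |
| 0.5 | 0.8 | 0.138 | 31.9% | 4.9% |
| 0.5 | 1.0 | 0.200 | 60.5% | 5.2% |
| 0.3 | 0.2 | 0.008 | 5.0% | 4.9% |
| 0.3 | 0.5 | 0.050 | 8.3% | 5.1% |
| 0.3 | 0.8 | 0.118 | 25.2% | 5.1% |
| 0.3 | 1.0 | 0.174 | 47.8% | 5.0% |

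Hand check of the third row by Fisher's z: atanh(0.138) × √117 = 0.1388 × 10.817 = 1.50, and 1 − Φ(1.96 − 1.50) is about 0.32. This agrees with the simulation.

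The p = 0.5 rows apply equally with randomised group as the factor, if balanced blocks give roughly equal groups. In that case d is the programme's effect on each measure.

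**Where it can arise**
- *First evaluation:* nobody has started medical treatment or the programme, so neither can have caused a correlation. Tumour type, stage or existing medication still could.
- *Second and third evaluations:* treatment has started or ended, and programme exposure differs by group.
- *Fourth and fifth evaluations:* treatment history still differs. EG2's eight fortnightly sessions begin 15 days after the news that treatment has ended, so they finish near the fourth evaluation: 15 + 7 × 15 = 120 days.

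**If evaluations were combined.** The plan does not propose this, but does not exclude it. For two unrelated measures, each with within-patient correlation ρ over five evaluations, the variance of the coefficient is inflated by 1 + (5−1)ρ². The error rate is 2(1 − Φ(1.96/√inflation)). For assumed ρ = 0.3, 0.5 and 0.7 the inflation is 1.36, 2.00 and 2.96, and the error rate is about 9%, 17% and 25%.

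**Cost of adjustment.** At N = 120 the critical |r| is 0.179 unadjusted, and 0.180, 0.182 or 0.183 with one, three or five covariate terms.

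**The case against.** The best defence is that the general rule comes first and covers everything. A partial correlation is a Pearson coefficient computed on residuals, and coefficients can also be computed within treatment strata. Either would satisfy both sentences. The same section names ANOVA without mentioning covariates, which suggests generic method labels under one rule. This stands. A reader might infer that the two sentences contradict each other and cannot both be followed; the documents do not support that.

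A second defence is that bias needs treatment to shift both measures. The documents give no such effects, the plan tries to limit patient variability, and a shift of 0.2 SD causes no inflation. This also stands. A reader might infer that confounded links will be reported; only that they can be is supported.

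Third, no stated aim is a biology–psychology correlation. The secondary aim is the programme's effect on the biological systems, which the repeated-measures analyses and ANOVA address. This limits the reach of the point but does not remove it.

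Two things remain on the most charitable reading. Applying the listed covariates would still leave out randomised group, and two analysts could run different analyses and both claim to have followed the plan.

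**Conclusion.** The point holds as a gap in the specified method. The correlation as named does not deliver the promised control, and the list of controlled variables leaves out randomised group while programme exposure differs. The consequence is conditional. At N = 120 with an even split, inflation is nil at 0.2 SD, modest at 0.5 SD (about 10%) and large from 0.8 SD (about 32%, then 60% at 1.0 SD). With a 30/70 split the rates are lower, reaching 48% at 1.0 SD. These sizes rest on assumed shifts and an assumed alpha. Received treatment cannot explain correlations at the first evaluation, and the pooling figures apply only if evaluations are combined. The effect is confined to the association analyses; the EG1 versus EG2 comparison is untouched.

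**What to change.** Replace the Pearson sentence with a specification along these lines:

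- Associations between physiological and psychological variables are estimated by partial correlations, or equivalent linear models, separately at each evaluation.
- Every evaluation is adjusted for treatment type (planned type at the first evaluation) and pharmacological treatment.
- Evaluations after treatment has started are also adjusted for treatment duration and randomised group. Duration is not used at the first evaluation, where none has accrued.
- If evaluations are ever combined, a repeated-measures correlation or a mixed model with a patient effect is used.

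Add treatment duration to VARIABLES as a recorded item. Medical and pharmacological treatment are already there.

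The cost is wording, one extra data item and a few degrees of freedom, plus some more if treatment type has many categories. General linear models are already planned in the named packages, so no new software is needed.
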